### **3. Study Objective**

The objective of the trial is to demonstrate the safety and effectiveness of the Cardiva Mid-Bore Venous Vascular Closure System (VVCS) in sealing femoral venous access sites and providing reduced times to ambulation (TTA) compared with manual compression at the completion of catheter-based procedures utilizing 6 – 12 Fr inner diameter procedural sheaths, with single or multiple access sites. This study will be considered a success from a statistical perspective if it meets both the Cardiva Mid-Bore VVCS superiority goal for the primary effectiveness analysis and the non-inferiority goal for the primary safety analysis as stated in Section 8.

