#### 9.2.3. Safety

##### Primary Safety Analysis

The primary safety analysis will be based on the 30-day limb incidence rate of combined major access site closure complications (see 7.3). Both the combined rate and individual complication incidence rates will be reported by treatment received as described in 8.1.2.

The statistical hypotheses are as follows:

- $H_0$ : Cardiva Mid-Bore VVCS rate – manual compression rate  $\geq 5\%$
- $H_A$ : Cardiva Mid-Bore VVCS rate – manual compression rate  $< 5\%$

A 2-sided 95% confidence interval will be constructed by the bootstrap re-sampling method, with patient as the sampling unit as opposed to the limb, for the VVCS – manual compression

major complication rate difference. This is to account for an unlikely correlation between two limbs of a patient with respect to major closure complications. One million bootstrap resampling simulations will be performed. For each simulation, stratified sampling with replacement (by randomization stratification factor) will be performed separately for the two study arms and the VVCS – manual compression (MC) major complication rate difference will be recorded. With one million simulations, a data distribution will be generated for the VVCS – MC major complication rate difference. With patient as the sampling unit, any data structure (independent or correlated) between the same patient's two limbs is preserved in this data distribution. If the 97.5th percentile of the distribution, i.e. the upper limit of the 2-sided 95% confidence interval for the VVCS – MC difference, is <5%, then the null hypothesis of a ≥5% higher VVCS complication rate will be rejected at a 2-sided 0.05 significance level. In this case the VVCS major complications rate will be considered non-inferior to that of the manual compression.

As an example to illustrate the actual study results required in order to accomplish this goal, assume the two limbs within each patient to be independent (highly likely) and a 2% (4/204) major complication rate is observed for the MC control treatment. The observed VVCS major complication rate must be ≤ 3% (6/204) in order for the 95% confidence upper limit for the difference to be <5%. This confidence interval calculation is based on Newcombe's method derived from Wilson scores. (*Ref: Newcombe RG, Interval Estimation for the Difference between Independent Proportions: Comparison of Eleven Methods, Statistics in Medicine, 17, 8 73-890, 1998*).

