### **9.3. Sample Size Justification**

#### Effectiveness

Based on a prior study (RESPECT), mean TTA for manual control is estimated at 7.2 hours. The same mean for Cardiva Mid-Bore VVCS is estimated at 5 hours including an outlier and at 4.3 hours excluding the outlier. With an estimated joint standard deviation of 5.4 hours, the power for reaching a statistically significant difference at 2-sided 0.05 level with a total sample size of 204 (102 per group) is 0.83 including the outlier in the calculation; the same power is 0.97 excluding the outlier.

Safety

For the purpose of sample size/power estimation, we will assume major access site closure complications to be independent between the two limbs of the same subject. Based on clinical experience this is the most likely scenario for these rare events. According to review of the VASCADE arterial VCS RESPECT study, the combined major complication rate by limb is estimated to be 2% for both VVCS and manual compression. With these assumptions, simulations were conducted using the R software for a sample size of 204 each for VVCS and manual compression patients. The power for the Newcombe 2-side 95% confidence upper limit to exclude 5% is approximately 0.88.

In order to evaluate the Newcombe method as an approximation to the proposed analysis method, i.e. bootstrap by patient, systematic comparisons were performed between the upper limit of Newcombe and bootstrap confidence intervals. Complication rates of 0% – 3% were selected for comparison, as this range is expected to cover great majority of the actual cases. The results are presented in the following table.

 IDE G100246

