data scenarios, 2 Newcombe limits were  $> 0.05$ . For each of bootstrap Sim 1 and Sim 2, 1 limit was  $> 0.05$  but less than the corresponding Newcombe limit. Only in the unlikely scenarios of Sim 3, where 2 patients in the same treatment arm had complications in both legs, did Newcombe and bootstrap upper limits become similar. Therefore we conclude that for power estimation purposes the Newcombe confidence limit is a conservative but satisfactory approximation method; the actual bootstrap power may be slightly higher than the Newcombe estimate.

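### The primary safety bootstrap rule does not hold its stated 0.05 level, and the 6/204 example and 0.88 power describe a different test

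*Combined protocol and SAP*

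**What the plan says.** Section 3 makes the safety test necessary for success: "This study will be considered a success from a statistical perspective if it meets both the Cardiva Mid-Bore VVCS superiority goal" and also the safety non-inferiority goal.

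Section 9.2.3 (Primary Safety Analysis) sets an absolute margin of 5 percentage points on the 30-day per-limb rate. On method it states: "A 2-sided 95% confidence interval will be constructed by the bootstrap re-sampling method, with patient as the sampling unit as opposed to the limb". Resampling is done within each arm and stratified by 3 versus 4 access sites. If the 97.5th percentile of the resampled differences is below 5%, "the null hypothesis of a ≥5% higher VVCS complication rate will be rejected at a 2-sided 0.05 significance level".

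The same section illustrates the result needed when control has 4/204: "The observed VVCS major complication rate must be ≤ 3% (6/204) in order" for the upper limit to stay under the margin. It attributes that calculation to Newcombe's method.

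Section 9.3 (Safety) assumes 2% per limb in both arms and independent limbs, and reports: "The power for the Newcombe 2-side 95% confidence upper limit to exclude 5% is approximately 0.88". Table 5 compares Newcombe and bootstrap upper limits for 15 outcome pairs. The text after it concludes that Newcombe is conservative for power estimation and that "the actual bootstrap power may be slightly higher than the Newcombe estimate".

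**The concern.** A percentile bootstrap of a rare binary outcome reproduces the skewness and discreteness of the observed counts and tends to give an upper limit that is too low. Table 5 shows this: with 6 against 2 events the Newcombe limit is 0.054, which fails, while the bootstrap limit is 0.049 in Sim 1 and Sim 2, which passes. The plan reads the lower bootstrap limits only as a small gain in power. The same feature raises the chance of passing when the device truly is 5 points worse, and Sections 9.2.3 and 9.3 report no error rate at the margin.

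At stake is a success-defining safety claim. The low control rates, where the problem is worst, are plausible: the prior arterial trial that Section 9.3 cites for its 2% had no major complications in either arm (Section 1.4, Table 1: 0/275 and 0/142).

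**Working it through.** **Inputs.** 204 patients randomized 1:1 (Section 4.2), so 102 patients per arm. Eligibility requires 3 or 4 access sites with at most 2 per leg, so every patient contributes two limbs: 204 limbs per arm. The margin is 5 points, and the planning rates are 2% and 2% with independent limbs (Section 9.3).

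**Step 1: reproduce the plan's figures.** The Newcombe upper limit is (p1 − p2) + √[(u1 − p1)² + (p2 − l2)²], where u1 and l2 are Wilson 95% limits.

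- 6 vs 4: 0.0098 + √[(0.0627 − 0.0294)² + (0.0196 − 0.0077)²] = 0.0451, passes.
- 7 vs 4: 0.0147 + √[(0.0691 − 0.0343)² + (0.0196 − 0.0077)²] = 0.0515, fails.

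So 6/204 is the Newcombe cut-off, as stated. Weighting all outcome pairs by Binomial(204, 0.02) in each arm gives power 0.877, matching the stated 0.88. (Section 9.3 calls the 204 per arm patients; the figure reproduces only with 204 limbs. With n = 102 per arm it would be 0.479.)

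**Step 2: the planned bootstrap, exactly.** Resampling 102 patients with replacement gives a limb-event total whose distribution is the 102-fold convolution of the observed 0/1/2-limb frequencies. Let D* be the resampled difference in event counts. Since 10/204 = 0.0490 and 11/204 = 0.0539, the rule passes when P(D* ≥ 11) is at most 0.025. This reproduces Table 5, for example 6 vs 2: 0.049, 0.049 and 0.054 for Sim 1, 2 and 3.

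Against 4 control events, all in different patients, 7 VVCS events give P(D* ≥ 11) = 0.011 and a limit of 0.0441, which passes; 8 events give 0.028, which fails. For 7 vs 4 the limit is 0.0490 with one VVCS patient affected in both limbs and 0.0539 with two. Bootstrap power at 2% vs 2% is 0.94.

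**Step 3: error at the margin.** The true VVCS rate is set 5 points above control. A patient has 0, 1 or 2 affected limbs with probability (1 − p)², 2p(1 − p), p² under independence. With correlation ρ, both limbs are affected with probability p² + ρp(1 − p). The pass probabilities are summed over all outcomes.

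| One-sided error (nominal 2.5%), by control rate | 0% | 0.5% | 1% | 2% | 3% |
|---|---|---|---|---|---|
| Bootstrap, independent limbs | 5.4% | 5.6% | 4.9% | 4.2% | 3.8% |
| Newcombe, independent limbs | 2.3% | 2.0% | 2.1% | 2.3% | 2.3% |
| Bootstrap, correlation 0.3 | 6.4% | 6.3% | 5.6% | 4.6% | 4.1% |
| Newcombe, correlation 0.3 | 4.0% | 3.6% | 3.8% | 4.0% | 4.1% |

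The first cell can be checked by hand. With a 0% control rate the control count is always 0, and the bootstrap passes up to 5 VVCS events in different patients (P(D* ≥ 11) = 0.0115; 6 events give 0.0377). For X ~ Binomial(204, 0.05), P(X ≤ 5) = 5.5%. A few five-event outcomes with a bilateral patient fail, which leaves 5.4%. Newcombe passes up to 4 events: P(X ≤ 4) = 2.3%.

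**Step 4: stratified resampling.** The stratum split is not given. With assumed splits of 51/51 and 31/71 per arm and equal rates, simulation gave 5.2–5.6% at 0%, 4.7–4.9% at 1%, 4.2–4.3% at 2% and 3.8–3.9% at 3%, with power 0.94. Stratification does not change the result.

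**The case against.** The plan labels both the 6/204 example and the 0.88 power as Newcombe, tabulates both limits, and says bootstrap power may be higher. A disclosed, understated power is not an error in itself. That stands. What remains is that Section 9.2.3 presents 6/204 as a requirement, which it is not for the test to be run, and that 0.94 is more than slightly above 0.88.

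The two rules also differ little in events. With events in different patients and 0 to 6 control events, the bootstrap allows one more VVCS event than Newcombe, or two more when control has one. This is fair context, but one event is enough to move the error from about 2% to between 4 and 5.6%, and the plan claims a specific level.

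Reading the level as two-sided does not help: adding the opposite tail gives a total of about 6% at control rates of 0 to 2%, against 5%. Nor does limb correlation, the reason given for the bootstrap: at 0.3 the bootstrap's error rises further. The plan considers such correlation unlikely, so those rows are secondary.

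Finally, dropping the bootstrap as the decision rule is not the only way to correct the level. That also stands.

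**Conclusion.** The statement that the rule rejects at a 2-sided 0.05 level is wrong. At the plan's own 2% control rate, a device with a true 5-point excess would be declared non-inferior about 1.7 times as often as stated (4.2/2.5). At 0 to 0.5% it would be more than twice as often (5.4/2.5 to 5.6/2.5). The pass threshold and the power given do not describe the test that will decide the trial.

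This rests on 102 patients per arm with two limbs each, no dropout or crossover, and equal rates across strata. The correlations of 0.1 and 0.3 are assumptions, since the plan gives no value; the main result needs neither. The point should be settled before outcome data are seen.

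**What to change.** **Preferred.** Base the decision on the Newcombe upper limit with n in each arm replaced by n/(1 + r), and keep the patient bootstrap as supportive. Define r as one pooled estimate: the sum over all patients in both arms of (left-limb outcome − arm rate) × (right-limb outcome − arm rate), divided by the sum over the same patients of arm rate × (1 − arm rate). Floor it at 0, and set it to 0 if there are no events.

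- Error at control rates 0 / 0.5 / 1 / 2 / 3%: 2.3 / 1.9 / 2.1 / 2.2 / 2.2% with independent limbs; 2.6 / 2.1 / 2.2 / 2.3 / 2.3% at correlation 0.1; 3.1 / 2.4 / 2.4 / 2.4 / 2.4% at 0.3.
- Power at 2% vs 2%: 0.87 / 0.83 / 0.76 at correlation 0 / 0.1 / 0.3, against 0.94 / 0.92 / 0.87 for the bootstrap.
- Sensitivity of r: 6 vs 4 events with one bilateral VVCS patient gives r = 0.873/4.873 = 0.18, effective n = 204/1.18 ≈ 173 and a limit of 0.0490, which still passes.

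**Alternative.** Keep the bootstrap but require its 99th percentile to be below 5%. With independent limbs the error is 1.8–2.5% and the power about 0.88.

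Plain Newcombe, or requiring both plain Newcombe and the bootstrap to pass, is not recommended: at correlation 0.3 the two-limit rule still has 3.5–4.0% error.

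**Minimum.** If the 97.5th percentile rule stays, restate the significance level, the 6/204 example and the power for that test.

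**Cost.** SAP wording and a restated power calculation; no new data. With independent limbs, power stays close to the stated 0.88. The residual weakness of the preferred rule is about 3.1% error if the control rate is near zero and limbs correlate at 0.3.

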#### Secondary Safety Analysis

The combined incidence rate and individual complication incidence rates will also be reported by treatment received for access site closure related minor complications. Formal non-inferiority testing will not be conducted for minor complications.

Additionally, all reported adverse events will be summarized by treatment regardless of relationship to access site closure.

### **9.3. Sample Size Justification**

#### Effectiveness

Based on a prior study (RESPECT), mean TTA for manual control is estimated at 7.2 hours. The same mean for Cardiva Mid-Bore VVCS is estimated at 5 hours including an outlier and at 4.3 hours excluding the outlier. With an estimated joint standard deviation of 5.4 hours, the power for reaching a statistically significant difference at 2-sided 0.05 level with a total sample size of 204 (102 per group) is 0.83 including the outlier in the calculation; the same power is 0.97 excluding the outlier.

Safety

For the purpose of sample size/power estimation, we will assume major access site closure complications to be independent between the two limbs of the same subject. Based on clinical experience this is the most likely scenario for these rare events. According to review of the VASCADE arterial VCS RESPECT study, the combined major complication rate by limb is estimated to be 2% for both VVCS and manual compression. With these assumptions, simulations were conducted using the R software for a sample size of 204 each for VVCS and manual compression patients. The power for the Newcombe 2-side 95% confidence upper limit to exclude 5% is approximately 0.88.

In order to evaluate the Newcombe method as an approximation to the proposed analysis method, i.e. bootstrap by patient, systematic comparisons were performed between the upper limit of Newcombe and bootstrap confidence intervals. Complication rates of 0% – 3% were selected for comparison, as this range is expected to cover great majority of the actual cases. The results are presented in the following table.

 IDE G100246

**Table 5: Comparison of Newcombe and Bootstrap 95% CI Upper Limits**

Experimental			Control				2-sided 95% CI Upper Limit for p1-p2			
							Bootstrap (100k reps)**			
n1	x1*	p1*	n2	x2*	p2*	p1-p2	Newcombe	Sim 1	Sim 2	Sim 3
204	0	0.000	204	2	0.010	-0.010	0.010	0.000	0.000	NA
204	0	0.000	204	4	0.020	-0.020	0.002	-0.005	0.000	0.000
204	0	0.000	204	6	0.029	-0.029	-0.005	-0.010	-0.005	-0.005
204	2	0.010	204	0	0.000	0.010	0.035	0.025	0.029	NA
204	2	0.010	204	2	0.010	0.000	0.026	0.020	0.025	NA
204	2	0.010	204	4	0.020	-0.010	0.018	0.015	0.015	0.015
204	2	0.010	204	6	0.029	-0.020	0.010	0.005	0.010	0.010
204	4	0.020	204	0	0.000	0.020	0.049	0.039	0.044	0.049
204	4	0.020	204	2	0.010	0.010	0.040	0.034	0.039	0.044
204	4	0.020	204	4	0.020	0.000	0.032	0.025	0.029	0.034
204	4	0.020	204	6	0.029	-0.010	0.024	0.020	0.020	0.025
204	6	0.029	204	0	0.000	0.029	0.063	0.054	0.059	0.064
204	6	0.029	204	2	0.010	0.020	0.054	0.049	0.049	0.054
204	6	0.029	204	4	0.020	0.010	0.045	0.039	0.044	0.049
204	6	0.029	204	6	0.029	0.000	0.037	0.034	0.034	0.039

\**x1* and *x2* are numbers of major complications, *p1* and *p2* are proportions of major complications

\*\**Sim 1*: complication data are independent, i.e. all events occur in different patients

\*\**Sim 2*: In one case complications occur in both legs of a patient in the arm with higher complication rate, or in arm 1 (experimental) if rates are the same in both arms

\*\**Sim 3*: In two cases complications occur in both legs of the same patient in the arm with higher complication rate, or in arm 1 (experimental) if rates are the same in both arms.  
(Scenario only applicable when at least one arm has 4 or more events.)

The mean difference,  $p_1 - p_2$ , was reproduced in all 42 bootstrap simulations. It can be seen that the Newcombe method is conservative in that its 95% confidence upper limit was uniformly higher than or the same as the corresponding bootstrap upper limit in simulation scenarios Sim 1 and Sim 2, with independent and low correlation complication data between limbs respectively. Out of 15 complication

data scenarios, 2 Newcombe limits were  $> 0.05$ . For each of bootstrap Sim 1 and Sim 2, 1 limit was  $> 0.05$  but less than the corresponding Newcombe limit. Only in the unlikely scenarios of Sim 3, where 2 patients in the same treatment arm had complications in both legs, did Newcombe and bootstrap upper limits become similar. Therefore we conclude that for power estimation purposes the Newcombe confidence limit is a conservative but satisfactory approximation method; the actual bootstrap power may be slightly higher than the Newcombe estimate.

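### The planned percentile bootstrap for the primary safety test is anti-conservative: false non-inferiority is about 0.042 to 0.054 with independent limbs, against a nominal one-sided 0.025, and section 9.3 reads its lower limits as reassurance

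*Combined protocol and SAP*

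**What the plan says.** Section 9.2.3 (Primary Safety Analysis) sets the decision rule. Patients are resampled within arm and stratum, and the 97.5th percentile of the resampled rate difference is taken as the upper limit. If that limit is below 5%, "then the null hypothesis of a ≥5% higher VVCS complication rate will be rejected at a 2-sided 0.05 significance level". That is a one-sided error of 0.025. Section 3 makes this test one of two that must succeed.

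Section 9.3 does not compute power for that rule. It takes "the combined major complication rate by limb is estimated to be 2% for both VVCS and manual compression", states that "we will assume major access site closure complications to be independent between the two limbs of the same subject", and reports: "The power for the Newcombe 2-side 95% confidence upper limit to exclude 5% is approximately 0.88". Table 5 ("Comparison of Newcombe and Bootstrap 95% CI Upper Limits") is then used to link the two methods. The text says that Newcombe's limit is never below the bootstrap limit in Sim 1 (no patient with events in both legs) or Sim 2 (one such patient), and that only in Sim 3 (two such patients) "did Newcombe and bootstrap upper limits become similar". It concludes that "the Newcombe confidence limit is a conservative but satisfactory approximation method" and that bootstrap power may be a little above the Newcombe figure. Type I error is not mentioned.

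**The concern.** For a non-inferiority test, a systematically lower upper limit means more passes. Those passes are a gain in power if the error rate holds, and a safety problem if it does not. With about four events per arm, a percentile bootstrap has few distinct outcomes to resample and tends to give an upper limit that is too low.

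Table 5 shows this at 6 vs 2 events: Newcombe fails (0.054), while the planned bootstrap passes in Sim 1 and Sim 2 (0.049). The text counts the smaller number of bootstrap limits above 0.05 in the method's favour. What is at stake is a claim that the device's major complication rate is non-inferior, made more often than the stated significance level allows when the true excess is 5 points.

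The closing description is also incomplete. It mentions only that power may be higher, and it does not say that Table 5 prints bootstrap limits above Newcombe's in part of Sim 3.

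**Working it through.** **Inputs.** Margin 5 points, 97.5th percentile and patient as resampling unit (section 9.2.3). 2% per limb in both arms, independent limbs (section 9.3). 204 subjects randomized 1:1 (section 4.2), with at least 3 access sites and at most 2 per leg (section 5.1.1), so 102 patients = 204 limbs per arm. The documents give no limb correlation ρ; the values 0, 0.2 and 0.5 are assumptions. The 3- vs 4-site strata are not modelled because their split is not given.

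**1. The plan's own figure.** Newcombe upper limit = d + √[(u₁ − p₁)² + (p₂ − l₂)²], where u and l are Wilson limits. Summing over two Binomial(204, 0.02) arms, P(limit < 0.05) = 0.877, which matches the stated 0.88. With 102 per arm it is 0.479 and with 408 it is 0.996. So 204 means limbs per arm, although the text says "simulations were conducted using the R software for a sample size of 204 each for VVCS and manual compression patients".

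**2. Table 5.** All 15 Newcombe and all 42 bootstrap limits reproduce to printed precision from the exact percentile-bootstrap distribution. Example, 6 vs 2: d = 4/204 = 0.0196, u₁ = 0.0627, l₂ = 0.0027, so the Newcombe limit is 0.0196 + √(0.0333² + 0.0071²) = 0.0536. Bootstrap limit, Sim 1: 10/204 = 0.0490.

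Bootstrap limit relative to Newcombe, as printed:

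| | above | equal | below |
|---|---|---|---|
| Sim 1 | 0 | 0 | 15 |
| Sim 2 | 0 | 2 | 13 |
| Sim 3 | 6 | 4 | 2 |

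The six rows above are 4 vs 2 (0.044, Newcombe 0.040), 4 vs 4 (0.034, 0.032), 4 vs 6 (0.025, 0.024), 6 vs 0 (0.064, 0.063), 6 vs 4 (0.049, 0.045) and 6 vs 6 (0.039, 0.037).

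**3. Error rate, one case by hand.** Take true rates of 5% vs 0% and independent limbs. The control arm has no events. Newcombe passes with at most 4 VVCS events (limit 0.0493; 5 events give 0.0561). The bootstrap also passes with 5 events if all are in different patients (10/204 = 0.0490).

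- P(X ≤ 4), X ~ Binomial(204, 0.05) = 0.0231: Newcombe's error.
- P(X = 5) = 0.0323, and P(all five in different patients) = C(102,5)·2⁵/C(204,5) = 0.951.
- Bootstrap error = 0.0231 + 0.0323 × 0.951 = 0.054.

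**4. General enumeration.** Each patient has 0, 1 or 2 affected limbs, with P(both) = p² + ρp(1 − p). Multinomial probabilities for both arms are summed over all outcomes that pass. The last column requires both limits to be below 5%.

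False non-inferiority at the margin, for ρ = 0 / 0.2 / 0.5 (nominal 0.025):

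| True rates | Bootstrap | Newcombe | Both |
|---|---|---|---|
| 7% vs 2% | 0.042 / 0.045 / 0.048 | 0.023 / 0.034 / 0.052 | 0.023 / 0.033 / 0.044 |
| 6% vs 1% | 0.049 / 0.054 / 0.057 | 0.021 / 0.032 / 0.050 | 0.021 / 0.032 / 0.046 |
| 5% vs 0% | 0.054 / 0.062 / 0.066 | 0.023 / 0.034 / 0.054 | 0.023 / 0.034 / 0.054 |

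Power at 2% vs 2%:

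| ρ | Bootstrap | Newcombe | Both |
|---|---|---|---|
| 0 | 0.943 | 0.877 | 0.877 |
| 0.2 | 0.895 | 0.858 | 0.856 |
| 0.5 | 0.828 | 0.834 | 0.815 |

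Bootstrap power crosses 0.88 at ρ of about 0.27.

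**5. The plan's worked example.** Section 9.2.3 says that with 4/204 control events at most 6/204 VVCS events may be seen, and bases this on Newcombe (7 vs 4 gives 0.0515). Under the bootstrap rule, 7 vs 4 events in different patients gives 9/204 = 0.044 and passes. The example therefore describes a stricter rule than the one planned.

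**The case against.** The strongest reply is that section 9.3 speaks only about power estimation. It confines its uniform statement to Sim 1 and Sim 2, names Sim 3 as the exception, and makes no claim about type I error. All of that is correct. But the decision rule in section 9.2.3 does claim a significance level, and the enumeration shows that the rule does not hold it under the plan's own independence assumption.

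A reader might infer from Table 5 that 0.88 is a floor that fails, or that the safety test is underpowered. The documents do not support this:

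- The plan never calls 0.88 a floor. It is computed under stated independence, where bootstrap power is higher.
- The reversal covers half of the Sim 3 rows only. With Sim 2 included it is 6 of 27 correlated-limb entries.
- None of the six reversals changes a decision at 5%. In Sim 3 the limits above 0.05 are at 6 vs 0 and 6 vs 2, the same two rows that Newcombe fails.
- Power falls below 0.88 only above ρ of about 0.27. Newcombe's power falls with correlation too, and at ρ = 0.5 the two methods nearly agree (0.828 and 0.834).

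The plan considers correlation unlikely, and no figure in the documents contradicts that. A check is still reasonable: section 8.3 counts pulmonary embolism, a patient-level event, per limb in subjects with access in both legs, and does not say how it is assigned to limbs.

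It is also fair to say that Newcombe is no cure under strong correlation, since its own error reaches 0.050 to 0.054 at ρ = 0.5.

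**Conclusion.** The concern holds as an error-rate problem. With independent limbs, the planned rule declares false non-inferiority with probability 0.042 to 0.054, about 1.7 to 2.2 times the nominal 0.025 (0.042/0.025 and 0.054/0.025). At ρ = 0.5 the range is 0.048 to 0.066. The figure is largest when the control rate is near zero, and the RESPECT data in section 1.4, Table 1 show no major complications in 142 manual compression patients.

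The power gain over the stated figure is about 6.5 points under independence, more than a slight one, and it comes with this inflation. The conservative label is right for Sim 1 and Sim 2 and does not extend to Sim 3.

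This rests on 102 patients per arm with both limbs analysed, the same assumed ρ in both arms, and no stratification in the resampling.

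**What to change.** 1. **Section 9.2.3:** require the Newcombe (Wilson-score) upper limit to be below 5% as well as the bootstrap limit. Under independence this holds the error at 0.021 to 0.023 with power of about 0.88, and it agrees with the section's own worked example.
2. **Section 9.3:** confine the conservative statement to Sim 1 and Sim 2, state that the bootstrap limit exceeds Newcombe's in 6 of 12 Sim 3 rows, and report power and type I error of the actual decision rule, strata included, at assumed limb correlations of 0, 0.2 and 0.5. Correct the sample size wording to 204 limbs per arm.
3. **Cluster adjustment:** unadjusted Newcombe does not hold 0.025 under strong correlation. If an adjustment is wanted, specify how the correlation is estimated from about four events per arm, and simulate its operating characteristics before adopting it.

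**Cost.** Item 1 changes the primary safety success criterion, so it needs a protocol amendment before the data are analysed. Safety power under independence becomes about 0.88 instead of 0.94; at ρ = 0.5 it is 0.815 instead of 0.828. The sample size does not change. Items 2 and 3 need revised text and a short simulation.
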